9.1.2. Derived Pharmacokinetic Parameters

9.1.2.1. Non-compartmental Analysis

- The pharmacokinetic parameters for Part 1 will be calculated by standard non-compartmental analysis according to current working practices and using Phoenix WinNonlin, version 6.3 or later.
- All calculations of non-compartmental parameters will be based on actual sampling times.
- Pharmacokinetic parameters described in [Table 7](#) will be determined from the Cycle 1 plasma concentration-time data in Part 1 of the study separately for each analyte, as data permit.

Table 7 Derived Pharmacokinetic Parameters

Parameter	Parameter Description
AUC(0-t)	Area under the concentration-time curve from time zero to the time of the last quantifiable concentration (C(t)) will be calculated using the linear trapezoidal rule for each incremental trapezoid and the log trapezoidal rule for each decremental trapezoid.
AUC(0-τ)	Area under the concentration-time curve during the dosing interval
AUC(0-∞)	Area under the concentration-time curve extrapolated to infinity will be calculated as: $AUC = AUC(0-t) + C(t) / \lambda_z$
%AUCex	The percentage of AUC (0-∞) obtained by extrapolation (%AUCex) will be calculated as: $[AUC(0-inf) - AUC(0-t)] / AUC(0-inf) \times 100$
Cmax	Maximum observed concentration, determined directly from the concentration-time data for each cycle
tmax	Time to reach Cmax, determined directly from the concentration-time data for each cycle
Cτ, Ctrough	Trough concentration prior to the next dose for each cycle

Parameter	Parameter Description
$t_{1/2}$	Apparent terminal half-life will be calculated as: $t_{1/2} = \ln 2 / \lambda_{z}$
t_{last}	Time of last observed quantifiable concentration
CL	Clearance
V _{ss}	Volume of distribution at steady state
λ_z , λ_{z}	Terminal phase rate constant
Ae(0-24)	Urinary recovery of cys-mcMMAF within the 24-h collection period will be calculated as: Urine cys-mcMMAF concentration x 24-h urine volume
Fe	Fraction of cys-mcMMAF dose excreted in the 24-h collection period will be calculated as: Ae(0-24) / cys-mcMMAF dose

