
 Refer to Section 9.3.2.
Model Results Presentation

 Power Model 
 The mean slope and the corresponding 90% confidence interval for each parameter will be produced in tabular format. Comparative plots of individual PK parameters will be generated by treatment on linear and semi-logarithmic scales. Supportive SAS output from statistical analysis will be generated.

9.3.1.2. Assessment of Accumulation Ratio:

To assess the extent of accumulation following GSK2857916 repeat dosing, the observed accumulation ratio (Ro) for GSK2857916, total antibody, unbound antibody, and cys-mcMMAF will be determined as ratio of C_{max} and C_{trough} at steady-state to C_{max} and C_{trough} after the first dose, respectively, adjusted for any change in GSK2857916 dose.

$$Ro (C_{max}) = C_{max} C_{xD1} / C_{max} C_{1D1};$$

x = 3, 5;

$$Ro (C_{trough}) = C_{trough} C_{xD1} / C_{trough} C_{1D1};$$

x = 3, 5;

Preliminary pharmacokinetic data indicate that the pharmacokinetics for the third consecutive dose given at the planned interval will be at steady state. Therefore, based

on the study design, subjects who meet one of the following criteria will be at steady state:

- Subjects who receive the same dose without delay or change for Cycles 1, 2, and 3 (i.e., with dosing delays of ≤ 3 days). In this case, Cycle 3 represents steady state. Accumulation ratios are calculated as Cycle 3/Cycle 1.
- Subjects who receive the same dose without delay or change to Cycle 5. Accumulation ratio = Cycle 5/Cycle 1.
- Subjects who have a dose reduction or two by Cycle 3, but then dose is maintained at the same level and interval through Cycle 5. Cycle 5 represents steady-state pharmacokinetics, but dose adjustment is needed. Dose adjustment: multiply C_{max}/C_{trough} values by the ratio (starting dose level/Cycle 3-5 dose level). Accumulation ratio = adjusted Cycle 5/Cycle 1.

For the purpose of accumulation ratio analysis, C_{max} is defined as the EOI concentration at each cycle.

Exploratory analysis might be performed considering the effect of dose delay on the ratio.

Accumulation Ratio Assessment (Part 1 and Part 2)
Endpoint(s)

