For the purpose of analyte ratio analysis, Cmax is defined as the EOI concentration at each cycle, and Ctrough is defined as the concentration immediately prior to the next cycle dose.

To fit into the analysis model, the units of the analytes need to be converted from ng/mL or pg/mL to nM as below.

	Original unit	Operation	Converted unit
ADC	ng/mL	/152.1	nM
Total Antibody	ng/mL	/152.1	nM
Unbound Antibody	ng/mL	/152.1	nM
cys-mcMMAF	pg/mL	/1045	nM

Pharmacokinetic Statistical Analyses
Endpoint(s)

 Cmax, Ctau by analyte and cycle
Model Specification

 Repeated measures mixed effects analysis
Model Checking & Diagnostics

 Refer to Section 9.3.2
Model Results Presentation

 Graphical ratios at Cycle 1 Graphical ratio of analyte to cys-mcMMAF by cycle

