19. Collect cytokines at predose (within 30 minutes prior to SOI) and EOI (± 5 min) (even when infusion is interrupted or halted) to assess allergic reaction)
20. All ADA samples will be collected prior to each infusion
21. PK samples to be taken (in all subjects) for both GSK2857916 and cys-mcMMAF measurement: C1D1 at pre-dose (within 30 minutes prior to SOI), 0.5 h after the start of the infusion (SOI) (± 5 min), at the end of infusion (EOI) just before EOI, 1 h after EOI, 3 h after EOI (± 5 min), 8 h after EOI (± 15 min), 24h after EOI (± 1 h) (Day 2); C1D8 1 sample; C1D15 1 sample; C2D1, at pre-dose (within 30 minutes prior to SOI) and at the EOI (just before EOI); C3D1 at pre-dose (within 30 minutes prior to SOI) and at the EOI (just before EOI).
22. Collect 1 PK sample at each subject's final visit.
23. Pre-specified amounts of urine will be collected for PK analysis from the 24 hour urine collection at Screening, C2D1, C4D1, C7D1, C10D1, C13D1, and C16D1. Refer to Section 7.4.2 of the protocol for details.
24. Study drug administration ± 3 day window only
25. Prophylaxis with prednisolone phosphate 1% or dexamethasone 0.1% 1 drop QID x 4 days starting 1 day prior to treatment
26. Record subject's survival status and whether subsequent treatment for disease was given. Subject does not need to come in for visit.

Abbreviations:

ADA = Antibody Drug Antibody; ALP = alkaline phosphatase; BCVA = best corrected visual acuity; BNP = B-type natriuretic peptide; C1D1 = Cycle 1 Day 1, etc.; cfDNA = Circulating free DNA; CK = creatinine kinase; CRP = C-reactive protein; EM = extramedullary; EOI = End of Infusion; FLC = free light chain; PD = Pharmacodynamics; PK = Pharmacokinetics; QID = 4 times a day; SOI = start of infusion; SPEP = serum protein electrophoresis; UPEP = urine protein electrophoresis

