16. Sample(s) collected for analysis at central lab. The same sample will be used for BCMA (flow) and PD. On D8 only postdose PD assessment will be performed, if applicable (refer to footnote 18).
17. FISH testing at least for: t(4;14), t(14;16), 17p13del. FISH results from samples taken within 60 days prior to first dose are acceptable.
18. **Additional samples may be collected in some subjects (up to 6) for further exploration of PD.**
19. Archival tissue from up to 60 days prior to study is acceptable.
20. Collect sBCMA at C1D1 predose (within 30 minutes prior to SOI) and at EOI (± 5 minutes), C2D1 at predose (within 30 minutes prior to SOI) and at EOI (± 5 minutes).
21. Collect cytokines at predose (within 30 minutes prior to SOI) and EOI (± 5 min) (even when infusion is interrupted or halted) to assess allergic reaction
22. All ADA samples will be collected prior to each infusion
23. Flow cytometry performed central laboratory.
24. PK samples to be taken for both GSK2587916 and cys-mcMMAF measurement on C1D1, C2D1, C3D1, and C5D1 at predose (within 30 minutes prior to SOI) and at EOI (just before EOI).
25. Collect 1 PK sample at each subject's final visit.
26. Informed consent for optional genetics research should be obtained before collecting a sample.
27. Study drug administration ± 3 day window only.
28. Prophylaxis with prednisolone phosphate 1% or dexamethasone 0.1% 1 drop QID x 4 days starting 1 day prior to treatment
29. All participants should be followed for survival for 1 year from last subject last dose. and whether subsequent treatment for disease was given. Subject does not need to come in for visit. Participants who have completed treatment or the 3 month follow up visit (end of study) prior to amendment 5 will be reconsented for further follow up and survival status.
30. e-Diary to be completed at screening, then Days 1-7, 8, 15 of each treatment cycle. Upon implementation of the e-Diary, these assessments will be required.
31. OSDI and NEI-VFQ-25 to be administered during end of study treatment visit. Additional assessments for subjects who are experiencing corneal symptoms to be completed via telephone on a monthly basis for up to 1 year, or until resolution of symptoms (whichever comes first) during the follow-up period.
32. Exit interview to be performed within 21 days of end of study visit

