CUMAMTCT	Cumulative dose to TTECORTOX (mg)		For corneal toxicity that occurred on dosing days, the dose on the corneal toxicity day was not included in the cumulative dose calculation.	adex. adae
Q4CUMAMTCT	Quartile of CUMAMTCT	0,1,2,3		derived
Q5CUMAMTCT	Quintile of CUMAMTCT	0,1,2,3,4		derived
CUMAUCCT	Cumulative AUC to TTECORTOX (ug.day/mL)		(Cumulative dose to TTECORTOX)/Individual Clearance of ADC	popPK output, adae
Q4CUMAUCCT	Quartile of CUMAUCCT	0,1,2,3		derived
Q5CUMAUCCT	Quintile of CUMAUCCT	0,1,2,3,4		derived
TAAUCCT	Time-average AUC till TTECORTOX (AUC/day)		The area under the plasma ADC concentration–time curve (AUC) per day (AUC/day) will be derived for each patient using the available ADC dosing information, individual patient oral clearance (CL/F) values from the population pharmacokinetic model, and the time to the occurrence of the corneal toxicity.	popPK output, adae
Q4TAAUCCT	Quartile of TAAUCCT	0,1,2,3		derived
Q5TAAUCCT	Quintile of TAAUCCT	0,1,2,3,4		derived
CANCER	Cancer type	0 or 1	0=Multiple Myeloma, 1=BCMA positive Lymphomas If TRT01AN = 12, then CANCER=1, else	adsl

Column Header	Data Item	Codes	Derivation/Comments	Source data set
			CANCER=0	
AMT	Amount (in mg) of GSK2857916 given in first cycle		AMT = AVAL when PARAMCD=ALTDOS and AVISIT=CYCLE 1 DAY 1	adex
Q4AMT	Quartile of AMT	0,1,2,3		derived
Q5AMT	Quintile of AMT	0,1,2,3,4		derived
TOTAMT	Total dose received (mg)		TOTAMT = AVAL * WEIGHTBL; Get AVAL for PARAMCD=CUMDOSE	adex,adsl
Q4TOTAMT	Quartile of TOTAMT	0,1,2,3		derived
Q5TOTAMT	Quintile of TOTAMT	0,1,2,3,4		derived
IDOSE	GSK2857916 initial cycle dose (mg/kg)	>0	IDOSE=adex.TRT01A; strip off units	adex
Q4IDOSE	Quartile of IDOSE	0,1,2,3		derived
Q5IDOSE	Quintile of IDOSE	0,1,2,3,4		derived
CMAx	First dose Cmax of ADC – Observed EOI on Cycle 1 (ng/mL)			popPK output
Q4CMAx	Quartile of CMAx	0,1,2,3		derived
Q5CMAx	Quintile of CMAx	0,1,2,3,4		derived
MMAFCMAx	First dose Cmax of MMAF – Observed EOI on Cycle 1 (ng/mL)			popPK output
Q4MMAFCMAx	Quartile of MMAFCMAx	0,1,2,3		derived
Q5MMAFCMAx	Quintile of MMAFCMAx	0,1,2,3,4		derived
CTAU	First dose C _{tau} of ADC– Observed pre-dose on Cycle 2			popPK output
Q4CTAU	Quartile of CTAU	0,1,2,3		derived
Q5CTAU	Quintile of CTAU	0,1,2,3,4		derived
AUC	First dose AUC(0-inf) of ADC (ug.day/mL)		First dose (mg)/Individual Clearance of ADC	popPK output
Q4AUC	Quartile of AUC	0,1,2,3		derived
Q5AUC	Quintile of AUC	0,1,2,3,4		derived

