4.0181	PK	PK_T2	Summary of Results of Accumulation Ratio Assessment for GSK2857916 (Unbound Antibody) PK Parameter Cmax on Day 1 of Cycle 2, 3, 5 verses Cmax on Day 1 of Cycle 1 (Part 2 MM)	If data was not collected, present "No data to report"	SAC [A]
4.0183	PK	PK_T2	Summary of Results of Accumulation Ratio Assessment for GSK2857916 (Unbound Antibody) PK Parameter Cmax on Day 1 of Cycle 2, 3, 5 verses Cmax on Day 1 of Cycle 1 (Part 2 NHL)	If data was not collected, present "No data to report"	SAC
4.0190	PK	PK_T2	Summary of Results of Accumulation Ratio Assessment for cys-mcMMAF PK Parameter Cmax on Day 1 of Cycle 2, 3, 5 verses Cmax on Day 1 of Cycle 1 (Part 1)	By dose level	SAC [A]
4.0191	PK	PK_T2	Summary of Results of Accumulation Ratio Assessment for cys-mcMMAF PK Parameter Cmax on Day 1 of Cycle 2, 3, 5 verses Cmax on Day 1 of Cycle 1 (Part 2 MM)		SAC [A]
4.0193	PK	PK_T2	Summary of Results of Accumulation Ratio Assessment for cys-mcMMAF PK Parameter Cmax on Day 1 of Cycle 2, 3, 5 verses Cmax on Day 1 of Cycle 1 (Part 2 NHL)		SAC
4.0200	PK	PK_T2	Summary of Results of Accumulation Ratio Assessment for GSK2857916 (ADC) PK Parameter Ctrough on Day 1 of Cycle 2, 3, 5 verses Ctrough on Day 1 of Cycle 1 (Part 1)	By dose level	SAC [A]

CONFIDENTIAL

BMA117159

Pharmacokinetic: Tables					
No.	Population	IDSL / Example Shell	Title	Programming Notes	Deliverable [Priority]
4.0201	PK	PK_T2	Summary of Results of Accumulation Ratio Assessment for GSK2857916 (ADC) PK Parameter Ctrough on Day 1 of Cycle 2, 3, 5 verses Ctrough on Day 1 of Cycle 1 (Part 2 MM)		SAC [A]
4.0203	PK	PK_T2	Summary of Results of Accumulation Ratio Assessment for GSK2857916 (ADC) PK Parameter Ctrough on Day 1 of Cycle 2, 3, 5 verses Ctrough on Day 1 of Cycle 1 (Part 2 NHL)		SAC
4.0210	PK	PK_T2	Summary of Results of Accumulation Ratio Assessment for GSK2857916 (Total Antibody) PK Parameter Ctrough on Day 1 of Cycle 2, 3, 5 verses Ctrough on Day 1 of Cycle 1 (Part 1)	By dose	SAC [A]
4.0211	PK	PK_T2	Summary of Results of Accumulation Ratio Assessment for GSK2857916 (Total Antibody) PK Parameter Ctrough on Day 1 of Cycle 2, 3, 5 verses Ctrough on Day 1 of Cycle 1 (Part 2 MM)		SAC [A]
4.0213	PK	PK_T2	Summary of Results of Accumulation Ratio Assessment for GSK2857916 (Total Antibody) PK Parameter Ctrough on Day 1 of Cycle 2, 3, 5 verses Ctrough on Day 1 of Cycle 1 (Part 2 NHL)		SAC

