No.	Population	IDSL / Example Shell	Title	Programming Notes	Deliverable [Priority]
14.0121	PK	PK18	Median Plasma GSK2857916 (cys-mcMMAF) Concentration-Time Plots (Linear and Semi-Log) (Part 2 MM)		SAC [A]
14.0123	PK	PK18	Median Plasma GSK2857916 (cys-mcMMAF) Concentration-Time Plots (Linear and Semi-Log) (Part 2 NHL)		SAC
Dose Proportionality					
14.0130	PK	LIVER14	Scatter Plot of GSK2857916 (ADC), GSK2857916 (Total Antibody), GSK2857916 (Unbound Antibody), and cys-mcMMAF PK Parameters by Cycle 1 Dose (Part 1)	using log transformed value. for AUC(0-tau), Cmax, PK Parameter value as y-axis and Cycle 1 dose as x-axis; label x-axis with dose value. Use the format of mock up LIVER14, no reference line is needed.	SAC [A]
Accumulation Ratio					
14.0140	PK	PK_F1	Plot of Mean Accumulation Ratios for GSK2857916 Analytes (Linear and Semi-Log) (Part 1)	See example in page 7 of PPD  By dose level PRE: Ctau EOI: Cmax Add a reference line at 1 Plot Ro for Ctau and Cmax on	SAC [A]

Pharmacokinetic: Figures					
No.	Population	IDSL / Example Shell	Title	Programming Notes	Deliverable [Priority]
				different plots. Use "Ratio to C1 (EOI)" as y-axis label for Cmax; Use "Ratio to C1 (PRE)" as y-axis label for Ctau; Plot analytes: ADC, total antibody, unbound antibody, and cys-mcMMAF on the same plot.	
14.0141	PK	PK_F1	Plot of Mean Accumulation Ratios for GSK2857916 Analytes (Linear and Semi-Log) (Part 2 MM)	Add a reference line at 1	SAC [A]
14.0142	PK	PK_F1	Plot of Mean Accumulation Ratios for GSK2857916 Analytes (Linear and Semi-Log) (Part 2 NHL)	Add a reference line at 1	SAC
Analyte Ratio at Each Cycle 1					
14.0180	PK	PK_F1	Plot of Mean Analyte Ratios for GSK2857916 Analytes (Linear and Semi-Log) (Part 1)	See example in Page 6 of PPD  By dose PRE: Ctau EOI: Cmax Plot Ra for Ctau and Cmax on the same plot. Use "Analyte Ratio to cys-mcMMAF" as y-axis label	SAC [A]

Pharmacokinetic: Figures					
No.	Population	IDSL / Example Shell	Title	Programming Notes	Deliverable [Priority]
14.0181	PK	PK_F1	Plot of Mean Analyte Ratios for GSK2857916 Analytes (Linear and Semi-Log) (Part 2 MM)		SAC [A]
14.0182	PK	PK_F1	Plot of Mean Analyte Ratios for GSK2857916 Analytes (Linear and Semi-Log) (Part 2 NHL)		SAC

NOTES:

A. Indicates which displays will be generated for the reporting effort for multiple myeloma

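### Under the SAP's own definition of trough, the Cycle 3 and Cycle 5 trough accumulation and analyte ratios need samples that are never taken, and the display labels point to a different denominator

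*SAP*

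**What the plan says.** Section 9.3.1.2 sets the trough accumulation ratio as Ctrough CxD1 divided by Ctrough C1D1 for x = 3 and 5. For subjects dosed without change or delay through Cycle 3 it states that "Accumulation ratios are calculated as Cycle 3/Cycle 1". The same section places steady state at the third consecutive dose given at the planned interval.

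The displays add Cycle 2. Tables 4.0200 to 4.0233 cover "PK Parameter Ctrough on Day 1 of Cycle 2, 3, 5 verses Ctrough on Day 1 of Cycle 1 (Part 1" and its counterparts for Part 2 MM and Part 2 NHL. For Figure 14.0140, Section 16.12.11 instructs: "Use 'Ratio to C1 (PRE)' as y-axis label for Ctau".

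Trough is defined in three places, always as the value following the dose in question:

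- Table 7 in Section 9.1.2.1: "Trough concentration prior to the next dose for each cycle".
- Section 9.3.1.3, for the analyte ratios at X = 1, 2, 3, 5: "Ctrough is defined as the concentration immediately prior to the next cycle dose".
- Section 16.10.1, first-dose Ctau: "Observed pre-dose on Cycle 2".

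Section 9.3.2 also describes both terms of the trough accumulation ratio as troughs that come after the respective dose.

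From Cycle 2 on, the Part 1 footnote in Section 16.2.2.1 takes PK samples at "C2D1, at pre-dose (within 30 minutes prior to SOI) and at the EOI (just before EOI); C3D1 at pre-dose" and end of infusion, and at no later cycle. The Part 2 MM footnote in Section 16.2.3.1 samples "on C1D1, C2D1, C3D1, and C5D1 at predose (within 30 minutes prior to SOI" and at end of infusion. Section 16.2.3.3 gives Part 2 NHL the same pre-dose cycles.

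**The concern.** The formula and the table titles speak of a trough on Day 1 of a cycle, whereas the definitions attach a trough to the end of a cycle. The two conventions call for different blood samples, and the sampling schedule supports neither for every planned ratio.

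At stake is whether two programmers working from this SAP would produce the same trough ratios. One could return blanks for Cycles 3 and 5. Another could divide by a pre-drug value. A third could report the trough after the second dose under a Cycle 3 steady-state label. Repeat-dose trough is among the secondary PK parameters in Section 2.2, so these tables would be used to describe accumulation of the conjugate and of cys-mcMMAF.

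**Working it through.** The SAP states no figure to reproduce. The check matches each sample a ratio needs to the sampling days.

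**Inputs.** Pre-dose PK samples are taken at C1D1, C2D1 and C3D1 in Part 1, and at C1D1, C2D1, C3D1 and C5D1 in Part 2 MM and Part 2 NHL. The weekly schedules have other PK days, but Section 16.2.1 says weekly dosing was not explored. The final-visit sample is not tied to a next dose.

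**Reading A, the SAP's definition: trough of cycle x = pre-dose C(x+1)D1.**

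| Cycle | Sample needed | Part 1 | Part 2 MM | Part 2 NHL |
|---|---|---|---|---|
| 1 (reference) | C2D1 pre-dose | yes | yes | yes |
| 2 | C3D1 pre-dose | yes | yes | yes |
| 3 | C4D1 pre-dose | no | no | no |
| 5 | C6D1 pre-dose | no | no | no |

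Only Cycle 2 over Cycle 1 can be computed. The tables list it, but the formula (x = 3, 5) does not. Four analytes × three parts = 12 tables, and 12 × 3 comparisons = 36, of which 12 × 2 = 24 have no numerator. The trough analyte ratio has the same gap at X = 3 and X = 5.

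**Reading B, the labels taken literally: trough CxD1 = pre-dose CxD1.** The denominator is the C1D1 pre-dose sample, taken before any drug. It is expected to be non-quantifiable, so the ratio and its logarithm are undefined or depend only on an imputation rule.

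**Reading C, mixed: pre-dose CxD1 over pre-dose C2D1.** The Cycle 2 row is C2D1 over C2D1, which is 1 by construction. The Cycle 3 row is the trough after dose 2 over the trough after dose 1. The Cycle 5 row exists in Part 2 only and is the trough after dose 4 over the trough after dose 1.

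To size the mislabelling under Reading C, take a linear one-compartment model with a 21-day interval, r = exp(−ln 2 × 21 / half-life), and a trough after dose n proportional to 1 + r + … + r^(n−1). The half-lives are assumptions; the SAP gives none.

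| Assumed half-life (days) | r | Row labelled Cycle 3, Reading C (1 + r) | Cycle 3/Cycle 1 as defined (1 + r + r²) | Row labelled Cycle 5, Reading C | Cycle 5/Cycle 1 as defined |
|---|---|---|---|---|---|
| 5 | 0.054 | 1.054 | 1.057 | 1.058 | 1.058 |
| 10 | 0.233 | 1.233 | 1.288 | 1.300 | 1.303 |
| 14 | 0.354 | 1.354 | 1.479 | 1.523 | 1.538 |
| 21 | 0.500 | 1.500 | 1.750 | 1.875 | 1.938 |

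The Cycle 3 row is low by r²/(1 + r + r²): about 0.3%, 4%, 8% and 14%. The Cycle 5 row is low by at most (1.938 − 1.875)/1.938, about 3%.

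**Part 1, Cycle 5.** C5D1 is not sampled, so this row is empty under all three readings. The end-of-infusion sample is missing as well, which empties the Cycle 5 rows of the Part 1 Cmax tables (4.0160, 4.0170, 4.0180, 4.0190).

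**The case against.** Three stronger readings are tempting, and the SAP does not support them.

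A reader might infer that the plan instructs a division by zero. The lead-in to Section 9.3.1.2 refers to values following the first dose, Section 9.3.2 says the same of Day 1, and Section 16.10.1 takes the first-dose trough from Cycle 2 pre-dose. Together these show that the intended reference is pre-dose C2D1. Nor is zero a stated value. The population PK dataset rules anticipate non-quantifiable Cycle 1 pre-dose results, and the imputation guideline cited in Section 16.5.3 is not reproduced. What stands is that the titles and the axis label conflict with the definition.

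A reader might also infer that no trough ratio can be computed. By schedule, Cycle 2 over Cycle 1 is available in every part, and Reading C yields further values. It may well be what the authors meant. But it needs Day 1 to mean that day's pre-dose sample in the numerator and the next cycle's in the denominator, which the SAP nowhere says, and it conflicts with the numerator in Section 9.3.2.

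Finally, a reader might infer that a secondary endpoint is lost. Section 2.2 names repeat-dose trough as a PK parameter where data permit, not the accumulation ratio, and Tables 4.0050 to 4.0083 still summarise trough values. No efficacy or safety decision rests on these ratios.

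Section 9.3.1 makes these analyses conditional on sufficient data. That does not settle the point, because the samples are absent by design and not by chance.

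**Conclusion.** The point holds as a definition and labelling defect with a real sampling gap behind it. Under the SAP's definition, the trough accumulation ratios for Cycles 3 and 5 and the trough analyte ratios for X = 3 and 5 cannot be computed in Part 1, Part 2 MM or Part 2 NHL. This rests only on the definitions and the schedules. Two of the 12 tables (4.0221 and 4.0223, unbound antibody in Part 2) may in any case report no data, as their programming notes allow.

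The numerical error from the mixed reading is conditional. It is negligible if the half-life is short against the 21-day interval and reaches about 14% at an assumed 21 days. The Cmax ratios are otherwise sound, since end-of-infusion samples exist at C1D1, C2D1, C3D1 and, in Part 2, C5D1. The matter should be corrected before programming, but it does not threaten the trial's main conclusions.

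**What to change.** Name the sample for each trough, using only those already collected:

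- trough after dose 1 = pre-dose C2D1 (both parts);
- trough after dose 2 = pre-dose C3D1 (both parts);
- trough after dose 4 = pre-dose C5D1 (Part 2 only).

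A general rule such as the pre-dose value of the next sampled cycle should be avoided, because in Part 2 it would assign pre-dose C5D1 to both dose 3 and dose 4.

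Report the trough accumulation ratio as dose 2 over dose 1 (early accumulation, both parts) and dose 4 over dose 1 (steady state, Part 2). Section 9.3.1.2 also admits subjects whose dose was reduced by Cycle 3 and then held. If the reduction took effect at Cycle 3, dose 4 is only the second dose at that level, so the steady-state label needs a footnote or a restriction for them. Limit the trough analyte ratio to doses 1 and 2 in both parts, plus dose 4 in Part 2.

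Retitle Tables 4.0200 to 4.0233 and the Figure 14.0140 axis by dose number with pre-dose C2D1 as the reference, align the formula in Section 9.3.1.2, and drop the Cycle 5 rows from the Part 1 displays, Cmax included.

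The cost is SAP wording and display titles, with no new sampling. The downside is that fewer ratios are reported and Part 1 gives no steady-state trough ratio.
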